5.1.4 Formulation, Storage and Packaging – talimogene laherparepvec

Talimogene laherparepvec will be manufactured by Amgen

Talimogene laherparepvec will be presented as a sterile frozen liquid in a single-use 2.0cc Crystal Zenith vial with a gray Fluorotec®-coated chlorobutyl elastomer stopper, aluminum seal, and polypropylene cap. Each vial contains a minimum of 1.0 mL talimogene laherparepvec at either 10^6 PFU/mL or 10^8 PFU/mL concentrations. The supply for the 10^6 PFU/mL concentration will be packaged separately from the supply for the 10^8 PFU/mL concentration.

Talimogene Laherparepvec will be stored, prepared and handled as per Amgen's Pharmacy Information guide and local institutional guidelines.

Please refer to the Pharmacy Information Guide and local institutional guidelines for additional information regarding the formulation and packaging of talimogene laherparepvec.

5.1.5 Preparation and administration of talimogene laherparepvec

Preparation of Talimogene Laherparepvec:

- Amgen's pharmacy information guide and Local institutional guidelines will be followed with regards to the preparation of talimogene laherparepvec

Administration:

Talimogene Laherparepvec must be prepared and administered by a qualified healthcare professional.

The total volume of talimogene Laherparepvec to be prepared will be based on investigator evaluation of injectable lesions and estimation of the total volume needed based on the talimogene Laherparepvec Injection Volume Guideline Based on Tumor Size Table 3 (detailed information described in Pharmacy Information Guide). Prescribe the estimated total volume by rounding up to the nearest 1.0 mL.

The maximum volume of talimogene Laherparepvec administered at any dose is 4.0 mL for any individual lesion. The maximum dose in any one treatment is 4.0 mL. Use the maximum amount whenever lesions allow.

Table 3. Talimogene Laherparepvec Injection Volume Guideline Based on Tumor Size*

Tumor Size (longest dimension)	Maximum Injection Volume
> 5.0 cm	4.0 mL
> 2.5 cm to 5.0 cm	2.0 mL
> 1.5 cm to 2.5 cm	1.0 mL
> 0.5 cm to 1.5 cm	0.5 mL
≤ 0.5 cm	0.1 mL

Talimogene Laherparepvec should be injected into viable tissue if available and direct injection into necrotic tumor tissue should be avoided.

- Personal protective equipment (PPE) as per the local institutional guidelines for talimogene Laherparepvec is required during preparation and administration.

Drug Administration: Administer by intralesional injection into cutaneous, subcutaneous, and/or nodal lesions that are visible, palpable, or detectable by ultrasound

First dose: Inject up to 4 mL at a concentration of 10^6 (1 million) PFU/mL. Where clinically appropriate and feasible inject largest lesion(s) first; where feasible inject remaining lesion(s) based on lesion size until maximum injection volume is reached or all lesions have been treated.

Second dose and all subsequent doses (every three weeks after first dose): Inject up to 4 mL at a concentration of 10^8 (100 million) PFU/mL. All reasonably injectable lesions (cutaneous, subcutaneous and nodal disease that can be injected with or without ultrasound [US] guidance) should be injected with the maximum dosing volume available on an individual

dosing occasion. On each treatment day, prioritization of injections is recommended as follows where clinically appropriate and feasible:

- any new injectable tumor that has appeared since the last injection
- by tumor size, beginning with the largest tumor any previously un-injectable tumor(s) that is now injectable

Within the guidelines of the algorithm in Table 3, and the prioritization model above it is recommended that each lesion receive the maximum amount possible at each visit before moving on to the next lesion, subject to tumor-specific limitations (such as inability to inject the full amount into the lesion). Lesions should be injected until the maximum volume per day (4.0 mL) has been reached or there are no further injectable lesions, whichever comes first.

Manufacturer's and Local institutional guidelines for the preparation and administration of talimogene laherparepvec and the management of talimogene laherparepvec contaminated materials or surfaces will be followed.

5.2 Pembrolizumab

Information extracted from Pembrolizumab Prescribing Information, available at: http://www.accessdata.fda.gov/drugsatfda_docs/label/2014/125514lbl.pdf

5.2.1 Mechanism of action - Pembrolizumab

Pembrolizumab (formerly known as MK-3475 or lambrolizumab), is a highly selective humanized monoclonal IgG4-kappa isotype antibody against PD-1, that acts by blocking its interaction with PD-L1 and PD-L2. Pembrolizumab is currently approved by the FDA for the treatment of patients with advanced melanoma and disease progression following ipilimumab and, if BRAF V600 mutation positive, a BRAF inhibitor.

Binding of the PD-1 ligands, PD-L1 and PD-L2, to the PD-1 receptor found on T cells, inhibits T cell proliferation and cytokine production. Upregulation of PD-1 ligands occur in some tumors and signaling through this pathway can contribute to inhibition of active T-cell immune surveillance of tumors. Pembrolizumab is a monoclonal antibody that binds to the PD-1 receptor and blocks its interaction with PD-L1 and PD-L2, releasing PD-1 pathway-mediated inhibition of the immune response, including the anti-tumor immune response. In syngeneic mouse tumor models, blocking PD-1 activity resulted in decreased tumor growth.

The theoretical molecular weights of the heavy and light chains derived from the amino acid sequences, excluding glycosylation, are 49.4 kDa and 23.7 kDa, respectively. The antibody is heterogeneously glycosylated at asparagine 297 within the Fc domain of each heavy chain, yielding molecular weights typically ranging between 148.9 and 149.5 kDa, depending on the attached glycan chains.

5.2.1 Non-clinical pharmacology - Pembrolizumab

Pembrolizumab is a potent and highly selective humanized mAb designed to block the interaction between PD-1 and its ligands, PD-L1 and PD-L2. Pembrolizumab potently blocks binding to both ligands with half maximal inhibitory concentration (IC50) values below 1 nM. Pembrolizumab enhances T cell responses in human donor blood cell cultures with an EC50 of ~0.1 to 0.3 nM. Pembrolizumab binds to cynomologus PD-1 with similar affinity, blocking

activity, and demonstrates equivalent enhancement of cynomologus T cell responses. It does not cross-react with rodent PD-1.

Pembrolizumab strongly enhances T lymphocyte immune responses in cultured blood cells from healthy human donors, cancer patients, and primates. The antibody potentiates existing immune responses only in the presence of antigen-receptor stimulation and does not nonspecifically activate all T cells. Using an anti-mouse PD-1 analog antibody, PD-1 blockade is demonstrated to significantly inhibit tumor growth in a variety of syngeneic murine tumor models. In experiments in mice, anti- PD-1 therapy is synergistic with chemotherapeutic agents, such as gemcitabine and 5-FU and this combination therapy results in increased efficacy, as well as complete regression rates *in vivo*.

The dissociation constants (KD) of pembrolizumab binding to human and cynomologus monkey PD-1 were determined by measurement of kinetic rate constants (on/off) in a solid phase format (ForteBiobiolayer-interferometry [BLI]). BLI measurements demonstrated that pembrolizumab binds human PD-1 with a fast association rate, dissociates very slowly, and has a high affinity of 29 pM (Table 2). The ability of pembrolizumab to block the binding of PD-1 ligands, PD-L1 and PD-L2, to human or cynomologus monkey PD-1 was measured using a competitive binding assay and detection by fluorometric microvolume assay technology (FMAT). Pembrolizumab potently blocks binding to both PD-1 ligands with IC₅₀ values below 1 nM.

5.2.2 Non-clinical toxicology - Pembrolizumab

Animal Toxicology and/or Pharmacology

In animal models, inhibition of PD-1 signaling resulted in an increased incidence of infections and enhanced inflammatory responses. *M. tuberculosis*-infected PD-1 knockout mice exhibit markedly decreased survival compared with wild-type controls, which correlated with increased bacterial proliferation and inflammatory responses in these animals. PD-1 knockout mice have also shown decreased survival following infection with lymphocytic choriomeningitis virus (LCMV). Administration of pembrolizumab in chimpanzees with naturally occurring chronic hepatitis B infection resulted in two out of four animals with significantly increased levels of serum ALT, AST, and GGT, which persisted for at least 1 month after discontinuation of pembrolizumab.

In the 1-month and 6-month toxicology study in cynomologus monkeys, pembrolizumab administered once a week and once every other week respectively, intravenously up to 200 mg/kg resulted in no adverse treatment related effects. The exposure multiple based on a predicted AUC 0-tau of 4464 $\mu\text{g} \cdot \text{day}/\text{mL}$ at the maximum anticipated human clinical dose of 10 mg/kg Q2W or Q3W is 15-fold at 200 mg/kg, the NOAEL for the 6-month monkey study. Additionally, in the tissue cross-reactivity study of pembrolizumab with human and monkey tissues demonstrated the expected on-target staining of the membranes of mononuclear leukocytes in both species. Off-target cross-reactivity staining was also noted in both species but was limited to cytoplasm of various cell types/tissues and the stroma (extracellular connective tissue matrix), and was considered related to the experimental method artifacts,

i.e. tissue processing for IHC, that are well recognized limitations of tissue cross-reactivity studies and, thus not considered toxicologically relevant.

Carcinogenesis, Mutagenesis, Impairment of Fertility

No studies have been performed to test the potential of pembrolizumab for carcinogenicity or genotoxicity. Fertility studies have not been conducted with pembrolizumab. In 1-month and 6-month repeat-dose toxicology studies in monkeys, there were no notable effects in the male and female reproductive organs; however, most animals in these studies were not sexually mature.

5.2.3 Pharmacokinetics - Pembrolizumab

The pharmacokinetics of pembrolizumab was studied in 479 patients who received doses of 1 to 10 mg/kg every 2 weeks or 2 to 10 mg/kg every 3 weeks. Based on a population pharmacokinetic analysis, the mean [% coefficient of variation (CV%)] clearance (CL) is 0.22 L/day (28%) and the mean (CV%) elimination half-life ($t_{1/2}$) is 26 days (24%). Steady-state concentrations of pembrolizumab were reached by 18 weeks of repeated dosing with an every 3-week regimen and the systemic accumulation was 2.1-fold. The peak concentration (C_{max}), trough concentration (C_{min}), and area under the plasma concentration versus time curve at steady state (AUC_{ss}) of pembrolizumab increased dose proportionally in the dose range of 2 to 10 mg/kg every 3 weeks.

Specific Populations: The effects of various covariates on the pharmacokinetics of pembrolizumab were assessed in population pharmacokinetic analyses. The CL of pembrolizumab increased with increasing body weight; the resulting exposure differences were adequately addressed by the administration of a weight-based dose. The following factors had no clinically important effect on the CL of pembrolizumab: age (range 18-94 years), gender, renal impairment, mild hepatic impairment, and tumor burden. The effect of race could not be assessed due to limited data available in non-White patients.

Renal Impairment: The effect of renal impairment on the CL of pembrolizumab was evaluated by population pharmacokinetic analyses in patients with mild (eGFR 60 to 89 mL/min/1.73 m²; n=210), moderate (eGFR 30 to 59 mL/min/1.73m²; n=43), or severe (eGFR 15 to 29 mL/min/1.73m²; n=2) renal

impairment compared to patients with normal (eGFR greater than or equal to 90 mL/min/1.73m²; n=221) renal function. No clinically important differences in the CL of pembrolizumab were found between patients with renal impairment and patients with normal renal function [see *Use in Specific Populations (8.6)*].

Hepatic Impairment: The effect of hepatic impairment on the CL of pembrolizumab was evaluated by population pharmacokinetic analyses in patients with mild hepatic impairment (TB less than or equal to ULN and AST greater than ULN or TB between 1 and 1.5 times ULN and any AST; n=59) compared to patients with normal hepatic function (TB and AST less than or equal to ULN; n=410). No clinically important differences in the CL of pembrolizumab were found between patients with mild hepatic impairment and normal hepatic function. KEYTRUDA has not been studied in patients with moderate (TB greater than 1.5 to 3 times ULN and any AST) or severe (TB greater than 3 times ULN and any AST) hepatic impairment [see *Use in Specific Populations (8.7)*].

5.2.4 Summary of clinical experience with pembrolizumab

The efficacy of pembrolizumab was investigated in a multicenter, open-label, randomized (1:1), dose-comparative, activity-estimating cohort. Key eligibility criteria were unresectable or metastatic melanoma with progression of disease; refractory to two or more doses of ipilimumab (3 mg/kg or higher) and, if BRAF V600 mutation-positive, a BRAF or MEK inhibitor; and disease progression within 24 weeks following the last dose of ipilimumab. The trial excluded patients with autoimmune disease; a medical condition that required immunosuppression; and a history of severe immune-mediated adverse reactions with ipilimumab, defined as any Grade 4 toxicity requiring treatment with corticosteroids or Grade 3 toxicity requiring corticosteroid treatment (greater than 10 mg/day prednisone or equivalent dose) for greater than 12 weeks. Patients were randomized to receive 2 mg/kg (n=89) or 10 mg/kg (n=84) of pembrolizumab every 3 weeks until unacceptable toxicity or disease progression that was symptomatic, was rapidly progressive, required urgent intervention, occurred with a decline in performance status, or was confirmed at 4 to 6 weeks with repeat imaging. Assessment of tumor status was performed every 12 weeks. The major efficacy outcome measures were confirmed overall response rate (ORR) according to Response Evaluation Criteria in Solid Tumors (RECIST 1.1) as assessed by blinded independent central review and duration of response. Among the 173 patients enrolled, the median age was 61 years (36% age 65 or older); 60% male; 97% White; and 66% and 34% with an ECOG performance status 0 and 1, respectively. Disease characteristics were BRAF V600 mutation (17%), elevated lactate dehydrogenase (39%), M1c (82%), brain metastases (9%), and two or more prior therapies for advanced or metastatic disease (73%). The ORR was 24% (95% confidence interval: 15, 34) in the 2 mg/kg arm, consisting of 1 complete response and 20 partial responses. Among the 21 patients with an objective response, 3 (14%) had progression of disease 2.8, 2.9, and 8.2 months after initial response. The remaining 18 patients (86%) had ongoing responses with durations ranging from 1.4+ to 8.5+ months, which included 8 patients with ongoing responses of 6 months or longer. One additional patient developed two new asymptomatic lesions at the first tumor assessment concurrent with a 75% decrease in overall tumor burden; Pembrolizumab was continued and this reduction in tumor burden was durable for 5+ months. There were objective responses in patients with and without BRAF V600 mutation-positive melanoma. Similar ORR results were observed in the 10 mg/kg arm.

As of 18-Oct-2013, 1,000 patients have been treated with pembrolizumab at several dose-schedules, including 10 mg/kg every 2 weeks. Pembrolizumab has been generally well tolerated, as expected based on preclinical findings and other anti-PD-1 monoclonal antibodies. As of 18-Oct-2013 no serious infusions reactions had been reported, however, since the potential exists in anti-PD-1 monoclonal antibodies, investigators should be vigilant to this possibility. There is no contraindication to further clinical investigation with pembrolizumab. Pharmacokinetics were as expected, based on pembrolizumab being an IgG mAb and based on preclinical data, which support dosing once every 2 or 3 weeks. Pembrolizumab monotherapy induces an ORR of 25%/27% in patients with ipilimumab-exposed melanoma by central independent RECIST and oncology review/investigator assessed irRECIST, respectively. Pembrolizumab monotherapy induces an ORR of 39%/43% in patients with ipilimumab-naive melanoma by central independent RECIST and oncology review/investigator assessed irRECIST, respectively. These responses are remarkably durable. The preliminary 1-year survival rate for patients, many of whom have had multiple therapies, including ipilimumab, who receive pembrolizumab is 81%. Pembrolizumab

monotherapy induces an ORR of 21%/24% in patients with previously-treated NSCLC by central independent RECIST/investigator assessed irRECIST, respectively, with these responses also remarkably durable. Preliminary data suggest higher levels of PD-L1 expression in tumors of NSCLC are associated with increased activity (ORR 67% by investigator assessed irRECIST/57% by central independent RECIST); additional data are required to define the optimal PD-L1 cut point. The most commonly reported treatment emergent AEs experienced are fatigue (43.8%), nausea (26.7%), cough (25.3%), pruritus (24.6%), diarrhea (22.3%) and rash (21.5%). Immune-related adverse events were reported in 21.4% of melanoma patients; most of these events (15.8%) were considered drug-related by the

investigator. The most commonly reported, immune-related adverse events across the dose-schedules are rash (3.2%), pruritus (2.9%), vitiligo (2.9%), hypothyroidism (2.7%), arthralgia (2.2%), diarrhea (2.2%), and pneumonitis (1.9%). Review of the overall benefit:risk ratio of pembrolizumab favors enrollment of eligible patients into clinical trials of pembrolizumab. The preliminary data suggest that a dose of pembrolizumab at 2 mg/kg Q3W is appropriate for patients with melanoma.

No formal pharmacokinetic drug interaction studies have been conducted with KEYTRUDA.

Additional identified risks, potential risks and adverse drug reactions associated to pembrolizumab are described in detail in section 11.3.

5.2.3 Formulation, Storage and Packaging - Pembrolizumab

Pembrolizumab will be manufactured by Merck.

Pembrolizumab is supplied as pembrolizumab 50 mg lyophilized powder in a single-use vial for reconstitution or as Pembrolizumab 100 mg/4ml Solution for Injection

Reconstituted and diluted solutions of pembrolizumab should be stored either:

- At room temperature for no more than 4 hours from the time of reconstitution. This includes room temperature storage of reconstituted vials, storage of the infusion solution in the IV bag, and the duration of infusion.
- Under refrigeration at 2°C to 8°C (36°F to 46°F) for no more than 24 hours from the time of reconstitution. If refrigerated, allow the diluted solution to come to room temperature prior to administration.

Product should not be frozen.

5.2.4 Administration of pembrolizumab

Pembrolizumab must be prepared and administered by a qualified healthcare professional.

Pembrolizumab at a dose of 200 mg will be administered intravenously on Week 1 and every 3 weeks (\pm 3 days) thereafter. When talimogene laherparepvec and pembrolizumab are administered on the same day, talimogene laherparepvec must be administered first.

Pembrolizumab infusion will be administered as a 30-minute intravenous infusion. Investigators should make every effort to target infusion timing to be as close to 30 minutes as possible. However, given the variability of infusion pumps from site to site, a window of -5 and +10 minutes is permitted (i.e., infusion time is 30 minutes: -5 min/+ 10 min). A central catheter is not required for infusion; however if a subject has a central venous catheter in place, it is recommended that it be used for the infusion. A 0.2 or 0.22 μ m in-line filter made of polyethersulfone (PES) must be used during administration to remove any adventitious particles. If the infusion set does not contain a 0.2 or 0.22 μ m in-line filter, it is recommended to use an extension line containing the filter.

6.0 CRITERIA FOR SUBJECT ELIGIBILITY

Describe the characteristics of the patient/subject population.

6.1 Subject Inclusion Criteria

Patients must fulfill all of the following criteria to be eligible for admission to the study:

- Male or female age \geq 18 years at the time of informed consent.
- Be willing and able to provide written informed consent/assent for the trial.
- Be willing to comply with treatment protocol
- Subjects must have a histologically confirmed metastatic and/or locally advanced inoperable sarcoma (metastatic/locally advanced cohort)
- For histology specific additional metastatic cohorts, patients must have undifferentiated pleomorphic sarcoma/myxofibrosarcoma, epithelioid sarcoma or cutaneous angiosarcoma.
- Subjects must have at least 1 injectable cutaneous, subcutaneous (superficial or deep) soft tissue or nodal lesion \geq 10 mm in longest diameter. Of note, bone lesions are not eligible for injection unless there is a soft tissue component that is amenable to injection. Injectable lesions must not be chosen from a previously irradiated field unless there has been radiographically and/or pathologically documented tumor progression in that lesion prior to enrollment. Subjects with locally advanced/metastatic sarcoma must have at least one prior line of systemic therapy (e.g. chemotherapy, immunotherapy, targeted or biological therapy) An exception to this criterion will be made for patients with sarcoma histological subtypes for which there is no known standard systemic therapy (e.g.,epithelioid sarcoma). Treatment naïve patients may be enrolled if they have refused standard systemic treatment. Prior adjuvant therapy will not count provided it was completed more than 6 months previously.
- Adequate performance status: ECOG 0 or 1/KPS 100-70%
- Adequate organ function determined within 3 weeks of treatment initiation, defined as follows:
 - I. Hemoglobin \geq 8.0 g/dl
 - II. Absolute neutrophil count \geq 1,000/mm³ (1.0 \times 10⁹/L)
 - III. Platelet count \geq 75,000/mm³ (75 \times 10⁹/L)
 - IV. Serum bilirubin \leq 1.5 \times ULN OR direct bilirubin \leq ULN for a subject with total bilirubin level $>$ 1.5 \times ULN

- V. Aspartate aminotransferase (AST) $\leq 2.5 \times$ ULN OR $\leq 5 \times$ ULN for subjects with liver metastases
- VI. Alanine aminotransferase (ALT) $\leq 2.5 \times$ ULN OR $\leq 5 \times$ ULN for subjects with liver metastases
- VII. Alkaline Phosphatase $< 5 \times$ ULN
- VIII. Albumin $\geq 2.5\text{mg/dL}$
- IX. Serum creatinine $\leq 1.5 \times$ ULN or a measured or calculated^a creatinine clearance $\geq 60\text{mL/min}$ for subject with creatinine levels $> 1.5 \times$ institutional ULN (Note: Creatinine clearance need not be determined if the baseline serum creatinine is within normal limits. GFR can also be used in place of creatinine or CrCl)
- X. International Normalized Ratio (INR) or Prothrombin Time (PT) $\leq 1.5 \times$ ULN unless subject is receiving anticoagulant therapy as long as PT or PTT is within therapeutic range of intended use of anticoagulants
- XI. Activated partial thromboplastin time (aPTT) $\leq 1.5 \times$ ULN unless subject is receiving anticoagulant therapy as long as PT and PTT is within therapeutic range of intended use of anticoagulants

^aCreatinine clearance should be calculated per institutional standard

- Female subject of childbearing potential should have a negative serum pregnancy testing at screening visit and within 72 hours prior to the first dose of study medication.

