9.0 PRETREATMENT EVALUATION

Screening

All aspects of the screening evaluation should be completed prior to entering the study, unless otherwise noted:

Within 30 days of study start:

- Confirmation of disease: documented presence of metastatic and/or inoperable, locally advanced sarcoma with at least one palpable lesion deemed suitable for direct intralesional injection of talimogene laherparepvec and at least one target lesion. The palpable lesion may be used as the target lesion for RECIST assessment if it meets the RECIST 1.1 criteria for a target lesion and no other appropriate target lesion exists.
- All patients enrolled in this study will undergo a new baseline biopsy where feasible
- Informed Consent

Within 3 weeks of study start:

- Full medical history, physical exam, assessment of performance status by KPS or ECOG status
- Review of concomitant medications
- Complete vital signs (pulse, blood pressure, temperature, respiratory rate) as well as weight and height. Height may be documented at any time prior to registration.
- Standard baseline imaging with CT scan of the chest (with or without contrast), abdomen and pelvis (with contrast where renal function permits) and MRI if applicable. Additional imaging for research purposes may also be performed where clinically appropriate.
- 12-lead electrocardiogram (EKG)
- Serum β -HCG pregnancy test for women with child-bearing potential. (within 72 hours)
- Complete blood count with differential, including lymphocyte and eosinophil count.
- Comprehensive metabolic panel (glucose, blood urea nitrogen, creatinine, sodium, potassium, chloride, bicarbonate, calcium, total protein, albumin, serum bilirubin, alkaline phosphatase, ASL, AST), phosphorus, magnesium, TSH, T4 free, amylase, lipase.
- Review of inclusion and exclusion criteria

Please refer to Study Calendar in Section 10 for additional information.

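### The albumin entry limit in section 6.1 is written in mg/dL; applied literally it has no effect, and nothing else in the protocol corrects it

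*Combined protocol and SAP*

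**What the plan says.** Section 6.1 opens by making every inclusion criterion binding: "Patients must fulfill all of the following criteria to be eligible for admission to the study". One criterion is organ function, introduced as "Adequate organ function determined within 3 weeks of treatment initiation, defined as follows" and followed by items I to XI. Item VIII is the albumin limit: "VIII. Albumin $\geq 2.5\text{mg/dL". Item I of the same list uses a different unit: "I. Hemoglobin \geq 8.0 g/dl".

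Albumin is measured at screening. The pretreatment evaluation (section 9.0) includes it in the metabolic panel: "calcium, total protein, albumin, serum bilirubin, alkaline phosphatase, ASL, AST), phosphorus, magnesium, TSH, T4 free, amylase, lipase". That entry names the test but gives no unit, limit or reference range.

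Three other provisions rely on the inclusion criteria:

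- Section 7.1 requires a signed, protocol-specific Eligibility Checklist.
- Section 9.2.1 makes Second Course retreatment conditional on meeting the safety parameters in the inclusion criteria.
- Section 16.3.2 treats a request to treat someone who fails an eligibility criterion as a prospective deviation that needs prior IRB/PB approval.

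**The concern.** An entry limit is useful only if some patients could fail it. Serum albumin is ordinarily of the order of grams per deciliter, so a floor of a few milligrams per deciliter looks a thousandfold too low. If the text is taken at its word, one of the eleven limits that define adequate organ function does nothing.

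What is at stake is the clarity of a binding criterion. As approved, the protocol treats a patient with very low albumin as eligible, so no deviation arises. The same non-functioning limit carries into the Second Course screen through its reference back to the inclusion criteria. A report that copies the eligibility criteria would also repeat a limit that was probably not intended.

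**Working it through.** **Inputs.**

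- Written limit: 2.5 mg/dL (section 6.1, item VIII).
- Conversion: 1 g = 1000 mg.
- Serum albumin range: 1.0 to 5.0 g/dL. This is an assumption, because the documents give no reference range. It is set wide so that it includes severely low values.

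**Step 1: the written limit in other units.** 2.5 mg/dL ÷ 1000 = 0.0025 g/dL, or 0.025 g/L.

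**Step 2: who passes as written.** Ratio = albumin in mg/dL ÷ 2.5.

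| Assumed albumin (g/dL) | In mg/dL | Ratio to written limit | Passes as written |
|---|---|---|---|
| 1.0 | 1000 | 400 | yes |
| 1.5 | 1500 | 600 | yes |
| 2.0 | 2000 | 800 | yes |
| 2.5 | 2500 | 1000 | yes |
| 3.5 | 3500 | 1400 | yes |
| 5.0 | 5000 | 2000 | yes |

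Even the lowest assumed value clears the limit 400 times over, so the conclusion does not depend on where in the range a patient falls.

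**Step 3: the same number in g/dL.** If the unit were g/dL (an assumption; the documents do not state the intended unit), the limit would be 2.5 × 1000 = 2500 mg/dL, and 2500 ÷ 2.5 = 1000 times the written one. The first three rows of the table would then fail.

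**Step 4: does another section correct it?** Albumin appears as a listed laboratory test in section 4.1 (follow-up of responders), section 9.0 (screening), section 10.2, footnote 6 of Table 6, and the end-of-study visit in section 13.0. Hypoalbuminemia appears in Table 9 as a laboratory abnormality seen with pembrolizumab. None of these gives an albumin limit or unit.

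**Step 5: does any design figure use it?** The response rule in section 14.1 depends only on n = 20, a cut-off of 3 responses, and rates of 5% and 30%. Recomputed, P(X ≥ 3 | 20, 0.05) = 0.075 and P(X ≥ 3 | 20, 0.30) = 0.965, in line with the stated type I error of 0.08 and 96% power. Albumin does not enter this calculation, the toxicity boundaries of 2/4, 3/8, 4/14 and 5/20, or the Table 15 intervals for 10 patients.

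**The case against.** The strongest reply is that this is an obvious slip with little practical effect. Patients are treated at a single center with its own laboratory units, and staff comparing 2.5 with a laboratory report would probably see what was meant. The other ten organ-function limits stand, as do the performance-status criterion and the exclusion for uncontrolled intercurrent illness. The Eligibility Checklist is not among the documents and may already carry a different unit. Section 16.3 says in one place that the study has been completed, although its entry for another analysis site still refers to the end of the study. If enrollment is over, a correction changes no first entry.

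Most of this stands, and it limits the point to what the text says. It does not remove the error. The criterion is binding, the approved wording decides who is eligible, and no other section supplies the right unit. Second Course re-entry, while the study remains open, still refers back to the list.

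A reader might go further and infer that patients with severe hypoalbuminemia could trip the toxicity stop or depress the 24-week response rate. The documents do not support that. The stopping boundaries belong to the first 20 patients, whose response results section 4.1 already reports, and the additional-cohort statistics restate no boundary. The rule also counts only treatment-related events that lead to discontinuation or a long delay. No section links albumin to those events or to response.

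**Conclusion.** Item VIII is wrong as written. The limit equals 0.0025 g/dL and, on the assumption that serum albumin lies between about 1 and 5 g/dL, every patient passes it. If the number was meant in g/dL, the written limit is too low by a factor of 1000. The use of g/dl for hemoglobin in the same list makes a unit slip the likeliest explanation, but the intended unit and limit are for the sponsor to state.

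The conclusion that nobody is excluded describes the text. It would be tempting to infer that unsuitable patients were enrolled, but nothing in the documents shows that any patient was wrongly admitted. The statistical design is untouched. This is a small, definite error in a mandatory criterion and is worth correcting.

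**What to change.** 1. The sponsor confirms the intended albumin unit and limit and corrects item VIII of section 6.1.
2. The study team checks that the Eligibility Checklist and the Second Course re-entry screen (section 9.2.1) use the corrected wording.
3. Baseline albumin already collected is compared with the confirmed limit. Any patient below it is reported descriptively, with the count and values. Such patients should not be recorded as protocol deviations on this ground, because they met the criterion as approved.

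The cost is a one-item amendment through the review route in section 16.3.1, a check of the checklist, and a look-up of existing screening results. No new data are needed and no analysis changes. The only downside is that an occasional enrolled patient may prove to be below the confirmed limit and will need a line in the report.
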